9.2 Diet, lifestyle and study restrictions

During the study, the subjects will be confined at the clinical centre as follows:

Period 1:

- from the evening preceding the first administration (study day -1) until the morning of day 3.

Period 2:

- from the morning of day 8 to the morning of day 9.
- from the morning of day 14 to the morning of day 17.

Subjects will be discharged from the study after final assessments (Final visit or ETV).

The subjects will not take any food or drinks (except water) for at least 10 h (i.e. overnight) before investigational product administration. On days 1, 8 and 14, subjects will remain under fasting conditions up to 5 h post-dose.

Standardised meals will be served at the clinical centre according to the schedule below:

- Day -1: standardised dinner;
- Day 1, Day 8, Day 14: standardised lunch at approximately 5 h post-dose, standardised dinner at approximately 13 h post-dose;
- Day 2 and Days 15/16: standardised breakfast, lunch and dinner

Water will be allowed as desired, except for 1 h before and 1 h after investigational product administration. Coffee, tea or food containing xanthines (i.e. coke, chocolate, etc.), alcohol and grapefruit will be forbidden during confinement starting 48 h before the first administration until the end of the study. Smoking is not allowed for the whole study duration.

Routine ambulant daily activities will be strongly recommended. Hazardous, strenuous or athletic activities will not be permitted.

10 DESCRIPTION OF SPECIFIC PROCEDURES

10.1 Physical examination

Full physical examinations will be performed at screening and final visit/ETV. Date of the physical examination, overall investigator's interpretation (as normal or abnormal and, if abnormal, clinically significant or not clinically significant) and clinically significant abnormalities (if any) will be reported in the individual CRFs.

All clinically significant abnormalities after the screening visit will be recorded as AEs.

10.1.1 *Body weight*

Body weight will be recorded at screening and final visit/ETV.

Subjects will be weighed (kg) lightly clothed without shoes. Height will be measured at screening only and Body Mass Index (BMI) will be recorded. BMI will be calculated as weight [kg]/(height [m] x height [m]).

10.1.2 *Vital signs*

Subjects' blood pressure and heart rate will be measured by the investigator or his deputy after 5 min at rest (sitting/supine position) at the following times:

- at screening
- on day 1, day 8 and day 14: at pre-dose and 2 h post-dose
- on day 5 and day 18: at 96 h post-dose
- on days 10-13: at pre-dose
- at ETV (if applicable).

10.1.3 *ECGs*

12-Leads ECGs will be performed (supine position) at screening and final visit/ETV.

Date/time of the ECG recording, overall investigator's interpretation (as normal or abnormal and, if abnormal, clinically significant or not clinically significant) and clinically significant abnormalities (if any) will be reported in the individual CRFs. All clinically significant abnormalities after the screening visit will be recorded as AEs. Hard copies of the ECGs will be attached to the CRF.

10.2 Clinical laboratory assays

Samples of blood and urine will be collected. The following laboratory analyses will be performed at the screening visit:

HAEMATOLOGY

Leukocytes and leukocyte differential count (percentage values and absolute values), erythrocytes, haemoglobin (conv. units), haemoglobin (IS units), haematocrit, MCV, MCH, MCHC, thrombocytes.

BLOOD CHEMISTRY

Electrolytes: sodium, potassium, calcium, chloride, inorganic phosphorus

Enzymes: alkaline phosphatase, γ -GT, AST, ALT

Substrates/metabolites: total bilirubin, creatinine, glucose, urea or BUN, uric acid, total cholesterol, triglycerides

Proteins: total proteins

Serum pregnancy test (women).

URINE ANALYSIS

Urine chemical analysis (stick): pH, specific weight, appearance, colour, nitrates, proteins, glucose, urobilinogen, bilirubin, ketones, haematic pigments, leukocytes

Urine sediment (analysis performed only if sediment is present): leukocytes, erythrocytes, flat cells, round cells, crystals, cylinders, mucus, bacteria

SERUM VIROLOGY

Hepatitis B (HBs antigen), Hepatitis C (HCV antibodies), HIV 1/2 (HIV Ag/Ab combo).

A urine drug test will be performed at the clinical centre at screening, using a urine multi-drug kit. The following drugs will be assessed: cocaine, amphetamine, morphine, cannabis, benzodiazepines, barbital.

A serum pregnancy test will be performed by the laboratory at screening, as listed above. Urine pregnancy test will be performed on day -1 of each study period at the clinical centre.

The same analyses, with the exception of urine drug test, virology and pregnancy test, will be performed at the final visit/ETV.

Date/time of samples collection, overall investigator's interpretation (as normal or abnormal and, if abnormal, clinically significant or not clinically significant) and clinically significant findings (if any) will be reported in the individual eCRFs. All clinically significant abnormalities after the screening visit will be recorded as AEs.

10.3 Sampling for pharmacokinetic analysis

10.3.1 *Venous blood sampling*

Venous blood samples (up to 10 mL) will be collected from a forearm vein at the following times:

- At pre-dose (0 h), 0.5, 1, 1.5, 2, 3, 4, 6, 8, 12, 16, 24, 36, 48, 72 and 96 h post-dose after the first single dose (days 1-5) and the last multiple dose (days 14-18)
- At pre-dose on days 10-13
- At pre-dose (0 h) and 0.5, 1, 1.5, 2, 3, 4, 6, 8, 12, 16 and 24 h post-dose after the first multiple dose (days 8-9)

Actual sampling times for each subject will be recorded in the individual CRFs. The actual sampling times should not exceed the recommended tolerance ranges presented in the following table. Any deviation outside the recommended ranges will be verified through Data Clarification Forms and, if confirmed, will be reported as protocol deviation, although it will not automatically lead to the exclusion of the concerned subjects from the PK set.

Table 10.3.1.1 Tolerance ranges for the scheduled sampling times

Sampling time	Tolerance range
Pre-dose (0)	Within 30 minutes before investigational product administration
0.5 h (30 min)	± 1 min
1, 1.5 h	± 3 min
2, 3, 4 h	± 5 min
6, 8, 10, 12, 16, 24, 36, 48, 72, 96 h	± 10 min

Blood samples for PK analysis will be collected using an indwelling catheter with switch valve. The cannula will be rinsed, after each sampling, with about 1 mL of sterile saline solution containing 20 I.U./mL Na-heparin. The first 2 mL of blood will be discarded at each collection time to avoid contamination of the sample with heparin.

The remaining 8 mL will be collected from the catheter and transferred with a syringe into heparinised tubes (Li-heparin).

Samples handling and processing is described in study specific lab manual.

10.3.2 *Analytics*

The concentration of safinamide in plasma samples will be determined at a certified analytical laboratory (to be designated). Analyses will be performed according to the general Principles of "OECD Good Laboratory Practices for testing of chemicals" C(81) 30 (final) and GCP.

The method validation report and the analytical report will be attached to the final report.

10.3.3 *Labelling, storage and transport of samples*

10.3.3.1 *Samples labelling*

Labels and labelling process are described in the study specific lab manual.

10.3.3.2 *Samples storage and transport*

During the study the samples will be stored at $\leq 70^{\circ}\text{C}$. At the end of each collection day, aliquots 1 and 2 will be stored in separate freezers.

All aliquots 1, packed in sufficient dry ice, will be shipped by an authorised courier from the clinical centre (China) to the analytical laboratory.

11 ASSIGNMENT OF STUDY TREATMENT

11.1 Randomisation

Randomisation will be used to minimize bias in the assignment of subjects to treatment cohorts, to increase the likelihood that known and unknown subject attributes (e.g., demographic and baseline characteristics) will be evenly balanced across treatment cohorts.

The randomisation schedule will be computer-generated by the CRO biostatistician using SAS®. The randomisation schedule will be attached to the final clinical study report.

11.2 Treatment allocation

Subjects will be randomised to two study cohorts to receive single and multiple doses of 50 mg safinamide (cohort 1), or single and multiple doses of 100 mg safinamide (cohort 2), according to the study randomised, parallel-group design.

On day -1, Period 1, subjects will be assigned a randomisation number, which will be used to assign the study treatment according to the randomisation schedule, as detailed above. Subjects who prematurely discontinue participation after randomisation will not be replaced.

11.3 Blinding

This is an open study. No masking procedure will be applied.

The open label design is considered appropriate for the primary objective of pharmacokinetic characterization, because PK properties and assessments are not prone to bias of observation by the investigators or the subjects.

12 EVALUATION PARAMETERS

12.1 Study variables

12.1.1 Primary variables

The following safinamide PK parameters will be determined on day 1 (after the first dose), on day 8 (after the first multiple dose) and on day 14 (after the last dose):

After single dose and first multiple dose (day 1 and day 8):

- C_{max} , t_{max} , AUC_{0-t} , and AUC_{0-24h}

After single dose only (day 1):

- K_{el} , $t_{1/2}$, $AUC_{0-\infty}$, V_d/F , Cl/F and MRT

After multiple dose (day 14):

- C_{max_ss} , t_{max_ss} , C_{min_ss} , $AUC_{0-t,ss}$, $AUC_{0-24h,ss}$, C_{ave_ss} , R_{acc} , $DF\%$, Vd_{ss}/F and Cl_{ss}/F

12.1.2 Secondary variables

- Treatment emergent adverse events (TEAEs), vital signs (blood pressure, heart rate), body weight, physical examinations, clinical laboratory parameters, ECG.

12.2 Pharmacokinetic assessments

12.2.1 Pharmacokinetic parameters

The following safinamide PK parameters will be measured and/or calculated with a Non-Compartmental Analysis (NCA) using Phoenix WinNonlin v6.3 (or higher).

After single dose and first multiple dose (day 1 and day 8):

- C_{max} : Maximum safinamide plasma concentration
- t_{max} : Time to achieve C_{max}
- AUC_{0-t} : Area under the concentration-time curve from single dose administration to the last quantifiable concentration time t
- AUC_{0-24h} : Area under the concentration-time curve in the tau interval (from single dose administration to 24 h post dose)

After single dose (day 1):

- K_{el} : Apparent terminal elimination rate constant, calculated, if feasible, from the slope of a log-linear regression using at least 3 last concentration $>$ LLOQ points
- $t_{1/2}$: Apparent terminal elimination half-life, calculated, if feasible, as $\ln 2/K_{el}$
- $AUC_{0-\infty}$: Area under the concentration-time curve extrapolated to infinity, calculated, if feasible, as $AUC_{0-t} + C_t/\lambda_z$, where C_t is the last measurable drug concentration
- V_d/F : Apparent volume of distribution associated with the terminal slope, calculated, if feasible, as $Dose/(AUC_{0-\infty} * K_{el})$

Cl/F:	Apparent total body clearance, calculated, if feasible, as Dose/AUC _{0-∞}
MRT:	Mean residence time, calculated, if feasible, as AUMC _{0-∞} /AUC _{0-∞} , were AUMC _{0-∞} is area under the moment concentration-time curve extrapolated to infinity

The sampling schedule is considered adequate if the ratio AUC_{0-t}/AUC_{0-∞} equals or exceeds a factor of 0.8 (i.e. if %AUC_{extra} is <20%) for more than 80% of the individual PK profiles. This assures that AUC_{0-t} covers a sufficient percentage of the theoretical total extent of exposure.

The quality of log-linear regression (and, consequently, the reliability of the extrapolated PK parameters) should be demonstrated by a determination coefficient $R^2 \geq 0.8$. Individual extrapolated parameters, when considered unreliable, will be reported as NC (not calculated).

After multiple dose (day 14):

C _{max_ss} :	Maximum safinamide plasma concentration at steady state
t _{max_ss} :	Time to achieve C _{max_ss}
AUC _{0-t,ss} :	Area under the concentration-time curve at steady state from the last dose administration to the last quantifiable concentration time t
AUC _{0-24h,ss} :	Area under the concentration-time curve at steady state in the tau interval (from the last dose administration to 24 h post dose)
C _{ave_ss} :	Average safinamide plasma concentration at steady state, calculated as AUC _{0-24h,ss} /tau (24 h)
R _{acc} :	Accumulation ratio, calculated as AUC _{0-24h,ss} / AUC _{0-24h}
DF%:	Peak-trough fluctuation over one dosing interval at steady-state, calculated as (C _{max_ss} - C _{min_ss})/C _{ave_ss} *100
V _{d,F_{ss}}	apparent volume of distribution at steady-state associated with the terminal slope, calculated, if feasible, as Dose/(AUC _{0-24h,ss} *K _{el})
Cl/F _{ss}	apparent total body clearance at steady-state, calculated, if feasible, as Dose/ AUC _{0-24h,ss}

12.3 Safety assessments

Safety and general tolerability of the investigational products will be based on TEAEs, physical examinations, including body weight, vital signs, ECGs and routine haematology, blood chemistry and urinalysis laboratory tests.

13 STATISTICAL METHODS

The data documented in this study and the parameters measured will be evaluated using classic descriptive statistics, i.e. geometric mean, geometric CV (%) (PK data only), arithmetic mean, SD, CV (%), minimum, median and maximum values for quantitative variables, and frequencies for qualitative variables.

Not available data will be evaluated as “missing values”. The statistical analysis of demographic and safety data will be performed using Statistical Analysis Software (SAS®) Version 9.3 or higher.

The pharmacokinetic parameters will be calculated using the actual recoded sampling times and non-compartmental methods with Phoenix WinNonlin (Version 6.3 or higher).

13.1 Analysis Sets

13.1.1 *Definitions*

A subject will be defined as screened after the signature of the informed consent, regardless of the completion of all the screening procedures.

A subject will be defined as eligible if he/she meets all the inclusion criteria and not meet any exclusion criteria. Otherwise he/she will be defined as a screen failure.

A subject will be defined as enrolled in the study if he/she is included into the interventional phase of the study. The enrolment will be performed through randomised allocation to a treatment cohort. An eligible but not enrolled subject will be defined as a reserve.

A subject will be defined as randomised in the study when he/she is assigned to a randomised treatment cohort.

The following analysis sets will be considered:

- Randomised set: all randomised subjects. This analysis set will be used for demographic, baseline and background characteristics.
- Safety set: all randomised subjects who receive at least one dose of the investigational medicinal product(s). This analysis set will be used for the safety analyses.
- PK set: all randomised subjects who fulfil the study protocol requirements in terms of investigational medicinal products intake and have evaluable PK data readouts, with no major deviations that may affect the PK results. This analysis set will be used for the PK analysis.

Each subject will be coded as valid or not valid for the Randomised set, Safety set and PK set. Subjects will be evaluated according to the treatment they actually receive.

13.1.2 *Reasons for exclusion from the PK set*

Reasons for the exclusion of subjects from the PK set are the following:

Before bioanalysis

- vomiting and diarrhoea after drug intake which could render the plasma concentration-time profile unreliable
- intake of concomitant medications which could render the plasma concentration-time profile unreliable
- AEs which could render the plasma concentration-time profile unreliable
- administration errors which could render the plasma concentration-time profile unreliable
- other events which could render the plasma concentration-time profile unreliable

If one of these events occurs, it will be noted in the CRF as the study is being conducted.

After bioanalysis

Exclusion of subjects on the basis of pharmacokinetic reasons is possible only for:

- subjects with non-zero baseline concentrations $> 5\%$ of C_{max} for single dose and first multiple dose (day 1 and day 8)

The samples from the subjects excluded from the PK set should still be assayed and the results listed. Subjects should not be excluded from the PK set if the AUC_{0-t} covers less than 80% of the $AUC_{0-\infty}$.

Any data excluded will be discussed in the CSR.

13.2 Sample size and power considerations

Twelve (12) healthy male and female Chinese volunteers / cohort (24 in total) will be included in the study in order to have at least 8 completers / cohort. Drop-out subjects will not be replaced. Since no hypothesis will be tested, no formal sample size calculation has been performed. The sample size of this study has been determined in agreement with the guidance issued by the Chinese Food and Drug Administration (CFDA) for clinical pharmacokinetic studies (1).

13.3 Demographic, baseline and background characteristics

Demographic and background characteristics will be examined according to qualitative or quantitative data. Qualitative data will be summarised in contingency tables. Quantitative data will be summarised using classic descriptive statistics. The baseline will be the last pre-dose measurement.

13.4 Analysis of pharmacokinetic parameters

A descriptive PK will be presented. The results will be displayed and summarised in tables and figures. Individual and mean curves (+SD at nominal times), indicating inter-subject variability, will be plotted. Data below the lower limit of quantification (BLQ) will be

considered as 0 in the calculations and presented as BLQ in listings and tables. As a consequence of BLQ(i.e. 0) values, calculated geometric means (if requested) could be null. For this reason, in the presence of any null value, the geometric mean will be reported as not calculated (NC).

13.5 Safety and tolerability evaluation

13.5.1 Adverse events

Adverse events (AEs) will be coded by System Organ Class (SOC) and Preferred Term (PT), using the Medical Dictionary for Regulatory Activities (MedDRA).

AEs will be classified as pre-treatment AEs (PTAEs) and treatment-emergent AEs (TEAEs), according to the period of occurrence, as follows:

- PTAEs: all AEs occurring before the first dose of investigational product and not worsening after the first dose of investigational product.
- TEAEs: all AEs occurring or worsening after the first dose of investigational product

Individual PTAEs and TEAEs will be listed in subject data listings. No summary table will be provided for PTAEs. TEAEs will be summarised by treatment and overall. The number and percentage of subjects with any TEAE and the number of TEAEs will be tabulated by SOC and PT, seriousness, relationship with investigational product and severity.

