9.1 Study visits and procedures

Each study subject completing the study will undergo 8 visits plus a final visit.

The study protocol foresees 2 periods: in the first one the investigational products are administered in single dose, in the second one in multiple doses. The single dose in the first period and the first dose in the second period are separated by a wash-out interval of 7 days. Maximum and minimum study duration will be 32 and 20 days, respectively, screening visit included.

The first subject first visit (FSFV) is defined as the 1st visit performed at the clinical centre by the 1st screened subject. The last subject last visit (LSLV) is defined as the last visit performed at the clinical centre (or a telephonic follow-up, if applicable) by the last subject, i.e. the last visit foreseen by the study protocol, independently of the fact that the subject is a completer or a withdrawn subject.

The following phases, visits and procedures will be performed:

➤ Screening phase

- Screening – visit 1: between day -14 and day -2
- Period 1 – visit 2: day -1

➤ Interventional phase

- Period 1 – visit 3: days 1-3: single dose and blood sampling for PK analysis
- Period 1 – visit 4: days 4-5: blood sampling for PK analysis
- Wash-out interval of 7 days
- Period 2 – visit 5: days 8-9: first multiple dose and blood sampling for PK analysis
- Period 2 – visit 6: days 10-13: multiple doses and blood sampling for PK analysis
- Period 2 - visit 7: days 14-17: last multiple dose and blood sampling for PK analysis
- Period 2 - visit 8: day 18: blood sampling for PK analysis

➤ Final phase

- Final visit/early termination visit (ETV). In case of early discontinuation, discontinued subjects will undergo an early termination visit (ETV)

Study schedule

	Day	Procedures/Assessments	Notes
Screening – Visit 1	From day -14 to day -2	
 ➤ Explanation to the subject of study aims, procedures and possible risks ➤ Informed consent signature ➤ Subjects' screening number assignment ➤ Demographic data and lifestyle recording ➤ Medical/surgical history ➤ Previous/concomitant medications check ➤ Full physical examination (body weight, height, vital signs, physical abnormalities) ➤ ECG recording ➤ Clinical laboratory analyses: haematology, blood chemistry, urinalysis, serum virology and serum pregnancy test (women) ➤ Urine multi-drug kit test ➤ Adverse events check ➤ Inclusion/exclusion criteria evaluation ➤ Eligibility evaluation 	

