9.2 Diet, lifestyle and study restrictions

During the study, the subjects will be confined at the clinical centre from the evening preceding the first administration (study day -1) until the morning of day 18.

Subjects will be discharged from the study after final assessments (Final visit or ETV).

The subjects will not take any food or drinks (except water) for at least 10 h (i.e. overnight) before investigational product administration. On days 1, 8 and 14, subjects will remain under fasting conditions up to 5 h post-dose.

Standardized meals will be served at the clinical centre according to the schedule below:

- Day -1: standardized dinner;
- Day 1, Day 8, Day 14: standardized lunch at approximately 5 h post-dose, standardized dinner at approximately 13 h post-dose;
- Day 2 to Day 5, Day 9 to Day 13, and Days 15 to 17: standardized breakfast (after PK sampling), lunch and dinner;
- Day 6 and Day 7: standardized breakfast, lunch and dinner;
- Day 18: standardized breakfast (after PK sampling).

Water will be allowed as desired, except for 1 h before and 1 h after investigational product administration. Coffee, tea or food containing xanthines (i.e. coke, chocolate, etc.), alcohol and grapefruit will be forbidden during confinement starting 48 h before the first administration until the end of the study. Smoking is not allowed for the whole study duration.

Routine ambulant daily activities will be strongly recommended. Hazardous, strenuous or athletic activities will not be permitted.

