13.5 Safety and tolerability evaluation

13.5.1 Adverse events

Adverse events (AEs) will be coded by System Organ Class (SOC) and Preferred Term (PT), using the Medical Dictionary for Regulatory Activities (MedDRA).

AEs will be classified as pre-treatment AEs (PTAEs) and treatment-emergent AEs (TEAEs), according to the period of occurrence, as follows:

- PTAEs: all AEs occurring before the first dose of investigational product and not worsening after the first dose of investigational product.
- TEAEs: all AEs occurring or worsening after the first dose of investigational product

Individual PTAEs and TEAEs will be listed in subject data listings. No summary table will be provided for PTAEs. TEAEs will be summarised by treatment and overall. The number and percentage of subjects with any TEAE and the number of TEAEs will be tabulated by SOC and PT, seriousness, relationship with investigational product and severity.

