14.8 AEs monitoring window

- Start of monitoring: from immediately after the signature of the informed consent
- End of monitoring: up to final study visit/ETV (observation window)

An AE occurring after the final visit/ETV and coming to knowledge of the investigator (e.g. during a follow-up assessment or by spontaneous reporting by study subjects) must be recorded only if it is an ADR, according to the investigator’s judgment.

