4.2 General Presentation Considerations

Each cohort has three periods (pre-treatment period, single dose period (Day 1) and multiple doses period (Day 8 to Day 18)) with a washout duration of 7 days between single dose period and multiple dose period. Period will be displayed for subject listings where applicable. ‘Baseline’ is defined as the last available assessment prior to the first dose of study treatment (per period when pre-dose assessment is available for both of the single dose and multiple dose periods). ‘End of Study’ is defined as the last available post-treatment assessment. ‘Study Day’ will be calculated relative to the first dose date of study treatment i.e. Study Day = Assessment Date -First Dose Date + 1 (+ 1 if assessment date is on or after the first dose date).

Continuous data will be summarized in terms of the mean, standard deviation (SD), coefficient of variation (CV) (%), median, minimum, maximum and number of observations, unless otherwise stated.

Continuous data that are expected to be skewed will be presented in terms of the maximum, upper quartile, median, lower quartile, minimum and number of observations. The minimum and maximum will be reported to the same number of decimal places as the raw data recorded in the database. The mean, median, lower quartile and upper quartile will be reported to one more decimal place than the raw data recorded in the database. The SD will be reported to two more decimal places than the raw data recorded in the database. The CV(%) will be presented to one decimal place. In general, the maximum number of decimal places reported shall be four for any summary statistic.

Categorical data will be summarized in terms of the number of subjects providing data at the relevant time point (n), frequency counts and percentages. Any planned collapsing of categories will be detailed in the SAP text and the data displays.

Percentages will be presented to one decimal place. Percentages will not be presented for zero counts. Percentages will be calculated using the number of subjects included in the corresponding set of subjects that is indicated in the title of the tables as the denominator. If sample sizes are small, the data displays will show the percentages, but any textual report will describe frequencies only.

Changes from baseline in categorical data will be summarized using shift tables where appropriate.

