4.11.1 Adverse Events

All AE data will be listed individually by subject. Only TEAEs will be included in the summary tables. Any PTAEs will be included in the data listings but will not be included in the summary tables of AEs.

AEs will be summarized on per-subject basis and per-event basis. A per-subject basis means that even if a subject reported the same event repeatedly (i.e., events mapped to the same PT) during the trial period, the event will be counted only once. A per-event basis will report the number of events.

An overview table will be summarized for the following categories:

- Any TEAEs
- Any TEAEs related to study drug
- Any severe TEAEs
- Any severe TEAEs related to study drug
- Any TEAEs leading to drug interruption
- Any TEAEs leading to drug withdrawal
- Any TEAEs with outcome of death
- Any TEAEs with outcome of death, related to study drug
- Any SAEs (including events with outcome of death)

- Any SAEs (including events with outcome of death), related to study drug
- Any SAEs leading to drug withdrawal

The following summaries will be produced:

- A summary of TEAEs by SOC, and PT
- A summary of TEAEs by PT
- A summary of the most common TEAEs by PT (reported by > 5% of subjects in any treatment cohort).
- A summary of TEAEs by seriousness, SOC and PT
- A summary of TEAEs by severity, SOC and PT
- A summary of TEAEs by causality, SOC and PT

AE summaries will be displayed by period (single dose and multiple dose) and ordered in terms of decreasing frequency in total column for SOC and PT within SOC, and then alphabetically by SOC and PT within SOC. For each subject and each adverse event, the worst severity recorded will be attributed and used in the by-severity summary. Similarly, the worst seriousness will be attributed and used in the by seriousness summary, the worst causality (most related to treatment) will be attributed and used in the by-causality summary. If severity, seriousness or causality is missing, no imputation will be applied.

A by-subject listing of all adverse events (including non-treatment-emergent events) will be provided. This listing will include: subject identifier, age, sex, ethnicity, treatment cohort, period, adverse event (SOC, PT, and verbatim term), start date, end date, severity, causality, seriousness, action taken, and outcome.

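### The SAP shows TEAE counts and percentages side by side for a 7-day single-dose period and a 10-day multiple-dose period, without time at risk and without saying where Days 2 to 7 belong (minor)

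*Protocol*

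**What the plan says.** Protocol 13.5.1, which reads the same in v3.0 as in the earlier versions, defines the measures: "The number and percentage of subjects with any TEAE and the number of TEAEs will be tabulated by SOC and PT". On grouping it says only this: "TEAEs will be summarised by treatment and overall". The protocol has no split by period.

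The split comes from SAP v2.0, section 4.11.1: "AE summaries will be displayed by period (single dose and multiple dose"). The counting units there are again plain tallies: "AEs will be summarized on per-subject basis and per-event basis". Under SAP 4.2, percentages are taken over the whole analysis set named in the table title, not over the subjects who reach the period.

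The windows follow from the schedule:
- **Start to start.** Protocol 9.1: "The single dose in the first period and the first dose in the second period are separated by a wash-out interval of 7 days".
- **End.** Protocol 14.8: "End of monitoring: up to final study visit/ETV (observation window"). The final visit is on Day 18, after the assessments 96 h after the Day 14 dose.
- **Labels.** SAP 4.2 names the periods as "single dose period (Day 1) and multiple doses period (Day 8 to Day 18"). Days 2 to 7 fall under neither label.

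Neither document plans an event rate, a subject-days denominator or a note that the two windows differ in length.

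**The concern.** A table with a single-dose column beside a multiple-dose column invites a reader to compare them. If one column is watched for longer, it collects more background complaints even when the drug does nothing. The trial has no placebo arm from which to judge the background. Safety and tolerability after single and multiple dosing is the secondary end-point, so a reader may take a higher multiple-dose column as a sign of accumulation when part of it is window length.

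The label in SAP 4.2 adds a programming ambiguity. An event on Day 4 could be put in the single-dose period, or treated as falling in the washout and left out of both columns. Two programmers could produce different tables from the same data.

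**Working it through.** **The protocol's own day arithmetic.** Protocol 9.1 gives a maximum and minimum duration of 32 and 20 days and a 7-day interval between the Day 1 and Day 8 doses. Counting without a day 0: 14 + 18 = 32, 2 + 18 = 20, 8 − 1 = 7, and (18 − 14) × 24 = 96 h. All agree.

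**Window lengths for a completer**
- Single-dose: Day 1 dose to Day 8 dose = 8 − 1 = 7 days.
- Multiple-dose: Day 8 dose to the Day 18 visit = 18 − 8 = 10 days.
- Ratio: 10/7 = 1.43. Counting Days 8 to 18 as 11 calendar days gives 11/7 = 1.57.

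The 7-day figure is the natural reading of the schedule, not SAP text. Taken literally, the SAP 4.2 labels cover 1 calendar day against 11.

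**Effect with no drug effect.** The documents give no background TEAE rate, so a constant rate r per subject-day is assumed and varied. With 12 subjects per cohort, all followed to the end, expected events over T days are 12 × r × T and the expected share of subjects with at least one event is 1 − exp(−rT).

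| Assumed r | Events, 7 d vs 10 d | Share of subjects | Subjects of 12 | Excess |
|---|---|---|---|---|
| 0.01 | 0.84 vs 1.20 | 6.8% vs 9.5% | 0.81 vs 1.14 | 0.33 |
| 0.02 | 1.68 vs 2.40 | 13.1% vs 18.1% | 1.57 vs 2.18 | 0.61 |
| 0.05 | 4.20 vs 6.00 | 29.5% vs 39.3% | 3.54 vs 4.72 | 1.18 |
| 0.10 | 8.40 vs 12.00 | 50.3% vs 63.2% | 6.04 vs 7.59 | 1.54 |

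The event ratio is 1.43 at every rate. The subject ratio falls from 1.41 to 1.26 as r rises. The excess in subjects has a ceiling: exp(−7r) − exp(−10r) is largest at r = ln(10/7)/3 = 0.119, where it is 0.435 − 0.305 = 0.131, or 12 × 0.131 = 1.6 subjects.

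**How often it would show.** Treat the two periods' subject counts as independent binomials. At r = 0.02 in a cohort of 12, the multiple-dose count is higher with probability 0.52, tied with 0.22 and lower with 0.26. With both cohorts pooled (24) the figures are 0.61, 0.14 and 0.25.

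**Dropout before Day 8.** Suppose d of 12 subjects complete the 7 days but do not receive the Day 8 dose, and the denominator stays at 12. Subject-days are then 84 against (12 − d) × 10, and at r = 0.02 the multiple-dose share is (12 − d)/12 × 18.1%.

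| d | Subject-days | Ratio | Share at r = 0.02 |
|---|---|---|---|
| 0 | 84 vs 120 | 1.43 | 13.1% vs 18.1% |
| 2 | 84 vs 100 | 1.19 | 13.1% vs 15.1% |
| 4 | 84 vs 80 | 0.95 | 13.1% vs 12.1% |

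**With person-time.** At r = 0.02 the rates are 1.68/84 and 2.40/120, both 2.0 per 100 subject-days. The background-only ratio becomes 1.00.

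**The case against.** **The protocol text is not at fault.** Its tables are by treatment and overall. Both cohorts follow the same schedule, so the randomised 50 mg versus 100 mg comparison has equal windows. This stands: the point belongs to SAP 4.11.1 and 4.2 and does not touch the dose comparison.

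**No single-dose versus multiple-dose comparison is planned.** The secondary end-point is to collect safety and tolerability data, no hypothesis is tested, and period may be no more than a way of arranging the table. This limits the weight. But the two columns will be printed and read together, so making them comparable is still worthwhile.

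**The distortion is small and uncertain.** It is an average effect under assumed rates. At 0.02 per subject-day the multiple-dose count in a cohort of 12 is tied or lower with probability 0.22 + 0.26 = 0.48. Losing 4 of 12 before Day 8 would reverse it, and that is the loss the sample size allows for (at least 8 completers). This stands too. It also shows that the raw percentage mixes window length with attrition, which is a reason to print the subject-days.

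**Person-time is only a partial remedy.** It removes the window effect only if the background rate is constant, and the periods also differ in number of doses (1 against 7) and in order. Post-dose laboratory tests, ECG and physical examination occur only at Day 18 or ETV, and clinically significant findings become AEs. In completers, anything first found there falls in the multiple-dose period, and dividing by days does not correct that. Rates would also be coarse: one event moves them by 1/84 = 1.2 or 1/120 = 0.8 per 100 subject-days. A footnote is needed for these reasons.

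**Lost events on Days 6 and 7.** A reader might infer from the visit schedule, which has scheduled AE checks on Days 1 to 5 and 8 to 18 only, that events on Days 6 and 7 are missed. The documents do not support this. Protocol 14.7 and 14.8 require recording of any AE from consent to the final visit. Under v3.0 subjects stay at the centre on those days (Protocol 9.2: "Day 6 and Day 7: standardized breakfast, lunch and dinner"), and an AE check follows at the Day 8 visit.

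**Conclusion.** The point holds as a minor one about presentation. The by-period TEAE tables in SAP 4.11.1 compare 7 days with 10 without allowing for it, and SAP 4.2 leaves Days 2 to 7 without an explicit period. If the background rate is constant, follow-up is complete and the drug has no effect, expected events are 1.43 times higher in the multiple-dose column. In subjects, the excess is about 0.3 to 1.5 per cohort of 12 over assumed rates of 0.01 to 0.10 per subject-day, and no more than about 1.6 at any constant rate.

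Two stronger readings should be set aside. One is that the tables will make multiple dosing look worse: this is a tendency on average, which chance or early dropout with a fixed denominator can cancel or reverse. The other is that the SAP 4.2 label removes events on Days 2 to 7 from the analysis: SAP 3.2.3.1 counts every AE after the first dose as treatment-emergent and SAP 4.11.1 lists them all, so what is missing is a rule for the column, not the data.

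**What to change.** In SAP 4.2 and 4.11.1:

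1. **State the boundaries.** Assign TEAEs from the Day 1 dose to before the Day 8 dose (or ETV) to the single-dose period, and those from the Day 8 dose to the final visit or ETV to the multiple-dose period.
2. **Change the denominator.** In by-period tables, take percentages over the subjects dosed in that period.
3. **Add time at risk.** Add subject-days at risk and events per 100 subject-days to each by-period TEAE table. The subject percentages will still reflect unequal windows, so the rates are what to compare.
4. **Add a footnote.** Give the window lengths (7 and 10 days for completers), and say that post-dose laboratory tests, ECG and physical examination occur only at Day 18 or ETV, which person-time does not correct.

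The cost is a few table rows and a footnote, from dose and AE dates already recorded. The rates will be imprecise at this sample size. SAP v2.0 is written against protocol v2.0 and SAP section 1 allows updates before database lock, so the change can go in with any revision that brings the SAP up to protocol v3.0. No added AE checks on Days 6 and 7 are needed.
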